3.4 Data included in the analysis

The data will be analyzed by Novartis and/or [REDACTED]. Any data analysis carried out independently by the investigator(s) should be submitted to Novartis before publication or presentation. It is planned that the data from participating centers in this protocol will be combined within each of the arms, so that an adequate number of patients will be available for analysis.

Data will be summarized with respect to demographic and baseline characteristics, efficacy observations and measurements, safety observations and measurements, [REDACTED], where applicable. Time to event data will be analyzed using the Kaplan-Meier methodology and will be presented as Kaplan-Meier plots and Kaplan-Meier estimates.

Efficacy and safety analyses will be conducted on all patient data, both from the core study and extension phase. Note that the analysis carried out at the end of the core study will be of primary importance with analysis at the end of the extension phase being exploratory only.

3.4.1 Core phase analysis

For the core analysis, the data cutoff will be the 12 month or end of core phase evaluation and the analysis will take place after the last randomized patient has completed the 12 Month evaluation, or discontinued the study treatment due to progression or start of new anti-cancer therapy.

Only data from the 12 month core phase will be used in the core analyses, any data from the extension phase will be excluded. For patients who do not enter extension phase, safety follow up data (if available) will be included in the core analyses.

All events with start date before or on the 12 month evaluation date and with an end date after the 12 month end date will be reported as '*continuing at the end of the core phase*'. The same rule will be applied to events starting before or on the 12 month evaluation date and not having documented end date. This approach applies, in particular, to adverse event and concomitant medication reports. For these events, the 12 month evaluation date will not be imputed and therefore will not appear in the listings.

Imputation of end date will be performed with the 9 or 12 month evaluation date when needed for specific analyses e.g. exposure and dose intensity computation.

3.4.2 Extension phase analysis

For each arm, a final analysis on all data collected, including data from the core phase – unless otherwise specified - will be performed once the last patient discontinues the study treatment. All this data will be listed.

Only PFS analyses and all safety analyses will be repeated at the end of the extension phase since no changes are expected to the core data after the core analysis is performed. A formal check will be carried to demonstrate no change, or to document if any changes. All TLFs will not be rerun during the formal check, if any change is detected in the data, then it will be documented in the CSR. All analyses and data reporting performed after extension phase is completed will be reported in the extension phase CSR only.

3.5 Patients and treatments

The number and percentage of patients in each analysis set and each stratum split by treatment group will be summarized using the total number of patients randomized as the denominator for percentages. A listing of this information will also be provided based on all randomized patients. This will include the population flags, whether they were included or excluded from that specific population.

Protocol deviations severity codes defined in VAP Module 3 will lead to patient classification into the analysis sets as follows:

Severity Codes	Actions
0	Exclude from all efficacy analysis (including FAS)
1	Exclude from Per-Protocol analysis

Table 1 - Analysis set exclusions based on severity codes

Analysis set	PD severity codes that cause a patient to be excluded	Non-PD criteria that cause a patient to be excluded
Full	0	Did not receive at least one dose of study drug
Safety	NA	Did not receive at least one dose of study drug, or did not have at least one post-baseline safety assessment
Per-Protocol	0, 1	NA

A frequency tabulation of the protocol deviations leading to exclusion from analysis sets will be presented based on the number of patients in the full analysis set along with an associated listing for the core phase analyses. This listing will include the severity, the deviation code and the related description. Protocol deviations will be re-evaluated at the end of extension phase, therefore frequency table will be rerun at the end of extension phase based on

cumulative data. A listing will also be created displaying all protocol deviations recorded during the whole study.

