10.1.1 Full Analysis Set

The full analysis set (FAS) consists of all patients who received at least one dose of study drug. Following the intent-to-treat (ITT) principle, patients will be analyzed according to the treatment and stratum they were assigned to at randomization.

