3.6 Full Analysis Set (FAS)

The full analysis set consists of all patients who received at least one dose of study drug. Following the intent-to-treat (ITT) principle, patients will be analyzed according to the treatment and stratum they were assigned to at randomization. Disposition, demography and analyses of disease history will be repeated at the time of extension phase analysis based on those subset of full analysis patients, who started extension phase.

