6.3.2 Statistical Hypothesis, model and analysis

Single-stage phase II trials are frequently undertaken to determine whether a new procedure or treatment is likely to meet a basic level of efficacy before comparing it with the standard technique in a larger randomized phase III trial. This study is of a single stage design, which is defined as follows. Let p_0 be the highest proportion of patients progression-free at Month 9 which would indicate that the procedure or treatment is clearly ineffective, and p_1 be the minimum required proportion of patients progression-free to show that the procedure or treatment is effective. The trial tests the null hypothesis H_0 that the proportion of patients progression-free, p , is less than or equal to p_0 against the alternative hypothesis H_1 that p is greater than or equal to p_1 . It consists of entering a predetermined number of patients and

deciding in favor of p_0 or p_1 based on the success rate observed by using an appropriate cut-off between p_0 or p_1 . In a single-stage design, if the number of responses is greater than or equal to $R+1$, the hypothesis that p is less than or equal to p_0 is rejected. If the number of responses is less than or equal to R , the hypothesis that p is greater than or equal to p_1 is rejected.

In this trial, p_0 and p_1 have been set equal to 0.20 and 0.45, respectively. Forty (40) patients are planned to be randomized in each treatment group. If the number of responses is 13 or more, the hypothesis that $p \leq p_0 = 20\%$ is rejected with a target alpha error rate of 5% and an actual alpha error rate of 4.3%; if the number of responses is 12 or less, the hypothesis that $p \geq p_1 = 45\%$ is rejected with an actual beta error rate of 4%.

In the case where more than 40 patients are randomized to one arm, the required number of responses to reject the null and alternative hypotheses will be computed using the methodology described in Fleming's paper [Fleming 1982]. R Codes below compute the cutoff (RstarPlus1) to reject the null hypothesis for different sample sizes.

For example, with 41 patients, the required number of responses to reject the null hypothesis is still 13 responses, and with 42 patients the required number is 14 responses.

```
fleming <- function(n){
p.0 <- 0.2
Z <- qnorm(0.95)
N <- n
s <- round(N * p.0 + Z * sqrt((N * p.0 * (1 - p.0)))) + 1
thres <- list(N = N , RstarPlus1 = s)
return(thres)
}

n <- 40:45
f <- sapply(n, fleming)
f

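### The SAP's severity-code-0 rule can take treated patients out of the full analysis set, which contradicts the all-treated definition in SAP 3.6 and protocol 10.1.1

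*SAP*

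**What the plan says.** SAP 3.5 sorts patients into analysis sets by severity codes for protocol deviations. The codes are defined in VAP Module 3, which is not among the documents. For code 0 the action is "Exclude from all efficacy analysis (including FAS". Table 1 repeats this: the Full row shows 0 in the column for deviation codes, and not having been dosed appears in a separate column. Code 0 therefore reaches patients who did receive study drug.

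Two other places define the same set differently. SAP 3.6: "The full analysis set consists of all patients who received at least one dose of study drug". Protocol 10.1.1: "The full analysis set (FAS) consists of all patients who received at least one dose of study drug". Both invoke the intent-to-treat principle, and neither mentions deviations. In the protocol, major violations act only through the per-protocol set (10.1.3).

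The FAS carries the primary analysis (protocol 10.4.2, SAP 6.3.2), the Bayesian comparison of arms (SAP 6.3.3), progression-free survival (7.1), disease control rate (7.2), objective response rate (7.5) and the two biochemical time-to-event endpoints (7.7, 7.8).

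**The concern.** A programmer who follows Table 1 and one who follows SAP 3.6 would build different analysis sets from the same data whenever a dosed patient carries a code-0 deviation. The set built from Table 1 would no longer be the one the protocol promises, because it would have lost patients for reasons arising after randomization.

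The setting makes this more than a matter of tidiness. The trial is open-label, response is read locally, and the conditions that earn code 0 are not visible in either document. The decision rule is a count against a cut-off, so a single patient can matter. The readable part of SAP section 2, which lists departures from the protocol, describes only a change in how confidence intervals are displayed. Part of that section is blacked out, so it cannot be said that this departure is undisclosed.

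**Working it through.** **Inputs.** SAP 6.3.2 fixes the two rates: "In this trial, p_0 and p_1 have been set equal to 0.20 and 0.45, respectively". The same section gives the planned size of an arm: "Forty (40) patients are planned to be randomized in each treatment group". At least 13 responses are needed among 40. From the Amendment 5 rationale in the protocol: 13 responders of 41 on pasireotide LAR, 14 of 42 on everolimus, 13 of 41 on the combination, and 124 patients randomized in total.

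**Reproducing the plan's figures.** With X binomial on 40 patients:

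- P(X ≥ 13 | p = 0.20) = 0.0432. The SAP says the null "is rejected with a target alpha error rate of 5% and an actual alpha error rate of 4.3" per cent.
- P(X ≥ 13 | p = 0.45) = 0.9614, so beta = 1 − 0.9614 = 0.0386. The SAP says the alternative "is rejected with an actual beta error rate of 4" per cent.

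Both agree. The SAP's formula for other sample sizes is: cut-off = round(0.20·N + z₀.₉₅·√(N·0.20·0.80)) + 1.

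- N = 40: 8.0 + 1.645 × √6.40 = 12.161, cut-off 13.
- N = 41: 8.2 + 1.645 × √6.56 = 12.413, cut-off 13. The SAP agrees: "with 41 patients, the required number of responses to reject the null hypothesis is still 13 responses".
- N = 42: 8.4 + 1.645 × √6.72 = 12.664, cut-off 14, also as printed in the SAP.
- N = 38 and 39: 11.656 and 11.909, cut-off 13 in both cases.

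**Was anyone removed in the core analysis?** 41 + 42 + 41 = 124, the number randomized. The reported denominators leave nobody out.

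**How much could one removal matter?** Every arm meets its cut-off with nothing to spare (13 against 13, 14 against 14, 13 against 13). The SAP can be read as setting the cut-off from the patients analysed or from the patients randomized, so both are shown.

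| Reported | Patient removed | Left | Cut-off, n analysed | Cut-off, n randomized | Decision |
|---|---|---|---|---|---|
| 13/41 (pasireotide LAR; combination) | progression-free | 12/40 | 13 | 13 | reversed on both |
| 13/41 (pasireotide LAR; combination) | non-responder | 13/40 | 13 | 13 | unchanged |
| 14/42 (everolimus) | progression-free | 13/41 | 13 | 14 | unchanged on the first, reversed on the second |
| 14/42 (everolimus) | non-responder | 14/41 | 13 | 14 | unchanged |

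**What is still to be analysed on this set?** SAP 3.4.2 repeats progression-free survival and safety at the end of the extension. SAP 7.7 and 7.8 also repeat duration of biochemical response and biochemical progression-free survival on cumulative data. The primary test is not among the repeats.

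**The case against.** The best defence is that the rule has had no visible effect and has little left to act on. The core analysis used every randomized patient. The primary test is not to be repeated, the remaining efficacy analyses are Kaplan-Meier summaries with no decision rule, and SAP 3.4 calls the end-of-extension analysis exploratory. Code 0 may also be very narrow, or may apply to no treated patient. All of this stands, and it limits the size of the point. It does not remove the contradiction: a narrow exception would still have to appear in the FAS definition, and it does not.

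A reader might also infer more than the documents support, in four ways.

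- *That dropping a failure can turn a failed arm into a success, for example 13/42 into 13/41.* No arm had 13/42. The example also needs the cut-off to follow the reduced set, whereas SAP 6.3.2 ties the recalculation to more than 40 patients being randomized. On that wording the cut-off stays at 14 and 13 responses still fail.
- *That any removal shifts the cut-off.* It is 13 throughout from 38 to 41 patients.
- *That codes are assigned by people who know the outcome.* This is plausible in an open-label trial, but neither document says who assigns them.
- *That the end-of-extension re-evaluation of deviations reopens the FAS.* SAP 3.5 links that re-evaluation to re-running a frequency table, and SAP 3.8 names only the per-protocol set as open to revision. Equally, nothing freezes FAS membership.

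**Conclusion.** The inconsistency is real and is plain on the face of the SAP. It should be corrected, but it is a defect in the rule with no shown effect on a reported result. The live exposure is the extension analyses of progression-free survival, duration of biochemical response and biochemical progression-free survival, together with any re-run of the core efficacy results.

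The case for caring beyond consistency is the zero margin. On either reading of the cut-off, the loss of one progression-free patient would reverse the decision for pasireotide LAR or for the combination. That reversal goes against efficacy, so the reported data do not support a reading in which the rule helped an arm to pass.

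This rests on two assumptions: that the counts in the Amendment 5 rationale are those of the primary analysis, and that Table 1 means what its separate columns imply. How many patients could ever carry code 0 cannot be estimated without VAP Module 3.

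**What to change.** In SAP 3.5, give code 0 the same consequence as code 1, namely exclusion from the per-protocol set only. Deleting just the bracketed mention of the FAS would not be enough, because the remaining words would still exclude the patient from every efficacy analysis. In Table 1, replace 0 by NA in the deviation column of the Full row. Align VAP Module 3 with both changes.

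If the sponsor needs a narrow exception, write its conditions into the FAS definition, list it in SAP section 2 as a departure from the protocol, and keep the all-treated result as primary.

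The cost is two table entries and a check of VAP Module 3. No new output is required: SAP 3.5 already calls for a listing of set membership for all randomized patients and a listing of all deviations. Since the reported denominators include every randomized patient, the core results would not change.

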3.6 Full Analysis Set (FAS)

The full analysis set consists of all patients who received at least one dose of study drug. Following the intent-to-treat (ITT) principle, patients will be analyzed according to the treatment and stratum they were assigned to at randomization. Disposition, demography and analyses of disease history will be repeated at the time of extension phase analysis based on those subset of full analysis patients, who started extension phase.

3.7 Safety Set

The safety set consists of all patients who received at least one dose of study drug and had at least one post-baseline safety assessment. Please note: the statement that a patient had no adverse events (on the Adverse Event CRF) constitutes a safety assessment. Patients who have received at least one dose of study drug but who have no post-treatment safety data of any kind would be excluded from the safety set. Patients will be analyzed according to the study treatment (regimen) they actually received. Patients who received, during the whole treatment period, a treatment different from the one assigned at randomization will be analyzed according to the actual treatment received. Patients who received a non-randomized treatment for part of the trial will be analyzed as having received both treatment arms i.e. will be counted in the Pasireotide LAR and everolimus group.

3.8 Per-Protocol Set

The per-protocol set consists of all patients from the full analysis set without major protocol violations. Appendix 1 of VAP module 3 lists all major protocol violations.

The per-protocol set definition will be finalized prior to database lock and might be revised prior to extension phase database lock after the review of protocol violations collected during the whole study.

3.9 Assessment windows, baseline and post-baseline definitions, missing data handling

3.9.1 Assessment windows

Patients will be assessed at baseline (day -28 to -1) and will then attend up to 16 visits during the core study with a separate assessment being completed at the end of the core study (EOCS) (12 months), either completion or early withdrawal. Those patients presenting with clinical benefit and not experiencing unacceptable toxicity at the 12 month visit will continue into the extension phase until progression occurs. They will attend visits every 3 months with a separate assessment being completed at the end of the extension phase (EOEP) when progression occurs, patient withdraws or two years after treatment start of the last evaluable patient. All patients who discontinue study treatment must have safety evaluations 56 days after the last dose of pasireotide LAR or everolimus, whichever comes last. This includes those who didn't enter extension phase due to disease progression at week 52. Endpoints (i.e. EOCS and EOEP) will be summarized as per scheduled visits. Any data from unscheduled

visits (Unsch), will be listed. Early withdrawal visits will continue to be displayed at the EOCS visit i.e. it will not be re-mapped to the most appropriate visit.

Visits will be labeled as follows: Baseline, Day 1, Day 15, Day 21, Day 29, Day 49, Day 57, Day 85, Day 113, Day 141, Day 169, Day 197, Day 225, Day 253, Day 281, Day 309, Day 337, EOCS, 3 Mths Extn, 6 Mths Extn, 9 Mths Extn, 12 Mths Extn, 15 Mths Extn, ..., EOEP, Safety FU, Unsch.

The tumor assessments will be time-slotted using the time windows displayed in Table 2.

Table 2 - Time windows for tumor assessments

Time Window	Planned Visit Timing	Time Window Definition
Week 12	Study Day 85 (Week 12)]0; 126] days or]0; 18] weeks
Week 24	Study Day 169 (Week 24)]126; 210] days or]18; 30] weeks
Week 36	Study Day 253 (Week 36)]210; 294] days or]30; 42] weeks
Week 48	Study Day 337 (Week 48)]294; 351] days or]42; 50] weeks
Week 52	Study Day 365 (Week 52)]351; 379] days or]50; 54] weeks
Week 64	Study Day 449 (Week 64)]379; 491] days or]54; 70] weeks
Week k	Study Day x (Week y) x= k*7+1 ; y=k]x-43; x+41] days or]y-6; y+6] weeks

Study Day 1 = start of study treatment date

Similarly to tumor assessments, week-based time windows [REDACTED]. If more non-missing results fall into a specific time window, then the one will be chosen which is closer to the optimal study day of the specific time window.

3.9.2 Baseline and post-baseline definitions

For *efficacy evaluations*, the last available assessment before or at date of start of study treatment is taken as “baseline” value or “baseline” assessment. In the context of baseline definition, the efficacy evaluations include also ECOG performance status.

For *safety evaluations* (i.e. laboratory and vital signs), the last available assessment before or at date of start of study treatment is taken as “baseline” assessment.

If patients have no value as defined above, the baseline result will be missing.

3.9.3 Missing data handling

Throughout the study reasonable attempts will be made to limit the amount of missing data. However the majority of missing data will not be imputed. The only exceptions to this are for the RECIST calculations, see the table in the Primary efficacy evaluation section and censoring for the time to analyses detailed in the secondary efficacy evaluation sections.

4 General Strategies of Data Presentation

All categorical data will be summarized by frequencies and percentages. Where categorical data is missing, a ‘Missing’ row will be included at the bottom with frequencies and percentages for it also presented.

Continuous data will be summarized with either standard descriptive statistics (i.e. the number of non-missing data points, arithmetic mean, standard deviation, minimum, median and maximum), or will be collapsed into categorical data and summarized as categorical data.

Day 1 is relative to the treatment start date and is calculated as date of interest – treatment start date + 1. For visits/events occurring prior to treatment start date the ‘+1’ will be excluded, so the day before day 1 is day -1.

5 Patient Disposition, background and demographic characteristics

5.1 Patient disposition

All patient disposition outputs will be performed on the full analysis set.

The number of patients who received study drug, completed the core study and entered extension phase will be summarized. For patients who discontinued their reason for discontinuing will be presented. This will be summarized for the core study and the extension phase separately.

A listing will include details of patients’ last known date of study medication, whether they completed or discontinued and the primary reason for any discontinuation for both the core study and extension phase (if applicable), whether the patient is followed up for post treatment evaluation and death date if applicable.

A separate listing will also be presented which only includes screening failure patients. This will include the reason for screening failure.

5.2 Demographics and baseline characteristics variables

Demographics and baseline characteristics will be summarized using the full analysis set. The demographics of age (both numeric and categorical (<65 & ≥65)), sex, race, body mass index and Eastern Cooperative Oncology Group (ECOG) performance status (World Health Organization (WHO)) at baseline will be summarized. A listing will also be provided summarizing this information along with the height (cm), weight (kg) and child-bearing potential for women.

An additional listing will provide details of the pregnancy test, both at screening and post-baseline (including extension phase pregnancy test results as well). This will include the visit, sample date, the method (serum, urine) and the result (negative, positive).

The baseline stratification factors (i.e. histologic grade and treatment line) will be cross-classified, tabulated and listed against the stratification factors actually used at randomization (contained in the IVRS dataset).

Diagnosis and extent of cancer will also be summarized and listed. This will include primary site of cancer (lung, thymus), KI67 index categories, functional status of tumor (functioning, non-functioning), histologic grade as recorded on the eCRF (typical, atypical), treatment line (first line, others) time since initial diagnosis of primary site in months, type of lesions at baseline (target only, non-target only, both target and non-target), the presence of metastatic disease (yes, No) and if present the location of this. Time since initial diagnosis of primary site will be calculated as the date of the baseline visit minus the dates of initial diagnosis of primary site divided by 30.4375. Partial dates will be handled in the following way: where the day is missing e.g. XXAPR74 then the day will be imputed as 01, e.g. 01APR74, where the date and month are missing XXXXX73 then the day will be imputed as 01 and the month as JAN, e.g. 01JAN73. A listing will also present this information along with the date of first diagnosis.

Relevant medical history/current medical conditions will be coded using the latest version of the Medical Dictionary for Regulatory Activities (MedDRA) and will be presented by system organ class and MedDRA preferred term. Separate summary tables will be provided for past medical condition and current medical condition. A current medical condition will be those on the CRF that are flagged as an active problem. A listing of all relevant medical history/current medical conditions will be presented. This will include reported term, preferred term and system organ class, the diagnosis/surgery date and whether or not it is still an active problem.

History of prior long-acting somatostatin analogue therapy will be summarized, identifying any use of octeotide or lanreotide, as well as summarizing exposure to prior somatostatin analogues, in terms of both summary statistics and categorical frequencies (<6 months, ≥6 months - <2 years, ≥2 years - <5 years, ≥5 years). Duration of exposure (months) will be calculated as (end date of somatostatin analogue therapy – start date of somatostatin analogue therapy + 1) / 30.4375. A listing summarising the long-acting somatostatin therapies will also be presented.

Prior antineoplastic therapies will also be summarized overall, and separately by therapy type (Medications (solid tumor), Radiotherapy, Surgery/local or regional therapy). The medications (solid tumor) table will include if any prior antineoplastic regimens occurred and

if so the number, setting and best response at last treatment. The radiotherapy table will summarize if any prior radiotherapy occurred and if so the location, along with the setting and best response at last radiotherapy. The surgery/local or regional therapy table will include if any prior surgery occurred, the time since last surgery, procedure at last surgery and whether there was any residual disease. All these summaries will be based on the full analysis set. Listings will also be provided for each of the therapy types separately. The listing for medications (solid tumor) will include regimen number, medication, route, setting, number of cycles, start date, end date, best response, the duration of response and the date of progression. The listing for Radiotherapy will include location, start date, end date, cumulative dose and unit, setting, best response, method and whether or not the patient had received radiotherapy to 30% or more of their bone marrow. The listing for Surgery/local or regional therapy will include the procedure, the date of surgery and the residual disease.

Basic demographic data, disease history, prior long acting somatostatin analogue therapy and prior antineoplastic therapy summaries (overall, surgery, radiotherapy and medication, where data is collected in core phase) will be repeated for extension phase analyses displaying data on only the subset of patients entering extension phase.

